All patients will have the following labs drawn on a daily basis for the first 5 days after randomization and then weekly while in the hospital: IL-6, CBC with differential, CMP, Triglycerides, Ferritin, Fibrinogen, ESR, CRP, LDH, CK, Troponin, and D-dimer. An additional IL-6 will be drawn prior to the first dose of study drug to establish a baseline. In addition if a patient is placed on ketamine these labs will be drawn for the 5 days following initiation of ketamine and then return to once a week. These labs are measures of general medical status, renal status, liver status, and markers of inflammation. The use of these labs is 2 fold, they may be used up front to help determine when a patient should have the dose of ketamine escalated and they will be reviewed retrospectively for the research to determine impact of

the study drugs. IL-6 in particular will only be looked at retrospectively as it is a send out test and the length of time to get results is 3-5 days. Each patient will have the following vital signs from the prior calendar day and related data recorded on a daily basis: maximum temperature, minimum temperature, maximum heart rate, minimum heart rate, maximum blood pressure (based on mean arterial pressure), minimum blood pressure (based on mean arterial pressure), maximum oxygen patient is on and the method of delivery, minimum oxygen patient is on and the method of delivery, maximum respiratory rate, minimum respiratory rate. The nurses and physicians participating in this study will also be looking for progression of oxygen requirements whenever they access the chart and the floor staff will be instructed to call the study team immediately for consideration of ketamine rescue.

After the first five days the labs will be collected once a week (every 7 days +/-1 day) until discharge. Any of these labs drawn by the treatment team will be collected if they match the timeframe of the study labs additional labs will not need to be ordered for the study.

For all patients we will collect medical history specifically including what COVID-19 symptoms were present and for how long, the date and time of the positive COVID test and what lab it was run at, demographics, concomitant medications on a daily basis, and any available cardiac markers including CK, troponin, myoglobin and echocardiography results.

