After discharge patients will be called once a week (+/- 3 days) for 1 month to determine their current health status and review their medication compliance. If at the 1 month mark the patient has not resolved their symptoms fully the calls will be extended for an additional month, once a week.

While the exact time the patient will remain in the study is unclear depending on duration of the admission and duration of symptoms, we expect it will be approximately 3 months on average.

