3.2 Measurements of Outcomes

Primary Outcome Measure:

1. Progression of oxygenation needs

Count of participants initially presenting with mild/moderate disease who progress to requiring advanced oxygenation (high flow nasal canula, non-rebreather, continuous positive airway pressure (CPAP), bilevel positive airway pressure (BIPAP), or intubation)

[Time Frame: up to 1 month]

Secondary Outcome Measure:

2. Renal failure

Count of participants who develop or experience worsened renal failure as defined by RIFLE criteria, a 5-point scale where the categories are labeled: Risk-Injury-Failure-Loss-End stage renal disease, with Risk being the least severe and End stage renal disease being the most severe. The criteria for determination of stage are factors of serum creatinine and urine output. Numbers of participants worsening one or more RIFLE stages will be reported.

[Time Frame: up to 1 month]

3. Liver failure

Count of participants who develop or experience worsened liver failure as defined by serum transaminases five times normal limits

[Time Frame: Daily times 5, then weekly]

4. Cytokine Storm

Count of participants who develop cytokine storm as measured by elevated markers of inflammation (elevated D-dimer, hypofibrinogenemia, hyperferritinemia), evidence of acute respiratory distress syndrome (ARDS) measured by imaging findings and mechanical ventilator requirements, and/or continuous fever (≥ 38.1 ° Celsius unremitting)

[Time Frame: 1 month]

5. Mortality

Count of participants who die from COVID-19

[Time Frame: up to 1 month post hospital discharge]

6. Length of hospital stay

Length of hospital stay in days

[Time Frame: 1 month]

7. Intensive Care Unit (ICU) admission

Count of patients admitted to the ICU at any time during index hospitalization

[Time Frame: 1 month]

8. Intensive Care Unit (ICU) duration

Length of ICU stay in days

[Time Frame: 1 month]

9. Intubation

Count of participants requiring intubation

[Time Frame: 1 month]

10. Intubation duration

Length of intubation, measured in days

[Time Frame: 1 month]

11. Time until recovery

Time measured in days from hospital admission to determination patient is stable for discharge

[Time Frame: 1 month post hospital discharge.]

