Sample Size Determination: We assumed that 20% of patients admitted to the hospital will show progression to requiring more oxygen, and that we want to detect if naltrexone reduces the progression rate to no more than 10%. With these assumptions, a sample size of 154 per arm (308 total) is required to have 80% power based on a two-sample t-test, using PASS 16.

Secondary Outcomes: To examine the potential impact of ketamine on mortality, we will use the chi-squared test to evaluate the hypothesis that mortality is reduced in the naltrexone arm. We will also estimate the difference in proportions using the Bayesian approach noted above. We will use a type 1 error rate of 0.05 for this secondary outcome.

For all remaining secondary outcomes, we will estimate the difference between the two arms and not test for differences between the two arms since these data will be used in planning future studies. For dichotomous outcomes (renal failure, liver failure, cytokine storm, and ARDS), we will use the Bayesian approach discussed for estimating the difference in proportions. We will use generalized linear models to estimate the difference in durations (number of days in ICU, number of days on a ventilator, and length of stay), evaluating the distribution to use based on the data. We will consider using the Poisson, negative-binomial, and normal distributions. We will use a Bayesian approach, using a flat prior on the difference in means parameter. We will calculate 99% credibility intervals for all of these secondary outcomes given the multiple outcomes being examined.

For statistical analysis the biostatisticians and Data analytics teams at Beaumont ([name] and [name]) will pull patients who were not on SINK, had COVID-19 with as close to a direct match to patients with similar profiles who were treated on the SINK study. The match to the patients on SINK will aim to compare the outcomes of the two groups, to see if there is a difference in the outcomes. The evaluation is a chart analysis aimed at focusing on the outcomes of the study.

Safety Measures:

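### The matched SINK versus non-SINK chart comparison sets no common rule for finding outcomes, so lab-defined events, and post-discharge deaths if call data are used, can be expected to differ with no treatment effect

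*Combined protocol and SAP*

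**What the plan says.** The Statistical Analysis section (the second section numbered 3.2) says that the biostatistics and data analytics teams "will pull patients who were not on SINK, had COVID-19 with as close to a direct match" to patients treated on the study. The purpose is stated as "The match to the patients on SINK will aim to compare the outcomes of the two groups", and the method as "The evaluation is a chart analysis aimed at focusing on the outcomes of the study". The section gives no list of outcomes for this comparison, no data source beyond the chart, and no lab or follow-up window.

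Section 3.1, Research Design, sets out how SINK patients are observed. A panel that includes IL-6, CBC, CMP, ferritin, fibrinogen and D-dimer is "drawn on a daily basis for the first 5 days after randomization and then weekly while in the hospital". Further, "if a patient is placed on ketamine these labs will be drawn for the 5 days following initiation of ketamine". Labs ordered by the treating team count if their timing fits, so that draws are not duplicated. Follow-up continues by telephone: "After discharge patients will be called once a week (+/- 3 days) for 1 month".

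Measurements of Outcomes (the first section numbered 3.2) defines liver failure by transaminases alone, renal failure by RIFLE stage (creatinine and urine output), and cytokine storm by D-dimer, fibrinogen and ferritin together with ARDS and/or persistent fever. Mortality carries the window "Time Frame: up to 1 month post hospital discharge".

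**The concern.** A matched comparison is fair only if an event has the same chance of being recorded in either group. Here one group is observed under a protocol schedule and the plan gives the other nothing comparable. Matching on patient profile does not repair this, because the difference lies in the measurement and not in the patients.

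This comparison also carries some weight. Both randomized arms receive ketamine on progression, and the mortality test that the plan links to ketamine compares the naltrexone and placebo arms, so it does not isolate ketamine. The matched comparison is the only planned one whose reference group was not assigned ketamine by the study, and readers will look to it for Aim 2. A detection difference there could hide a benefit, suggest harm or, under another scoring choice, suggest a benefit that does not exist.

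**Working it through.** The plan states no figure on this point, so there is none to reproduce. The check sets the sections side by side and then illustrates how far unequal detection could move a result. Every rate below is an assumption.

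**1. Where each outcome comes from**

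| Outcome | Depends on | Observation in SINK | Observation the plan gives controls |
|---|---|---|---|
| Liver failure | Labs only; its time frame is the study lab schedule | Protocol panel | Chart |
| Renal failure | Creatinine and urine output | Protocol panel and chart | Chart |
| Cytokine storm | Three lab markers, ARDS, fever | Protocol panel and chart | Chart |
| Death to 1 month after discharge | Follow-up after discharge | Chart and weekly calls | Chart |
| ICU admission, intubation, length of stay | Hospital events | Chart | Chart |

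The first four rows differ by design. The last does not.

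**2. Lab frequency.** Suppose an abnormality lasts d days and labs are drawn every k days. Capture probability = min(1, d/k). Take d = 2.

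- Daily draws: 1.00.
- Routine draws every 3 or 4 days (assumed): 2/3 = 0.67 or 2/4 = 0.50.
- SINK to control ratio in the daily-lab periods: 1/0.67 = 1.5 or 1/0.50 = 2.0.
- Weekly phase, if SINK is scored only on the study schedule: 2/7 = 0.29, ratio 0.29/0.67 = 0.43 or 0.29/0.50 = 0.57. The direction reverses.
- Onset spread evenly over an assumed 14-day stay without ketamine: (5 + 9 × 0.286)/14 = 0.54, ratio 0.54/0.67 = 0.81 or 0.54/0.50 = 1.08.
- Routine labs also drawn daily and scored alike: ratio 1.0.

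**3. Effect on a comparison.** Observed rate = true rate × detection probability. Assume a true rate of 20% in both groups, 95% detection in SINK, and a two-sided test at 0.05. The plan names no test and no size for this comparison, so 154 and 308 per group are used only because they are the trial's per-arm and total sample sizes.

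| Detection in controls | Observed, SINK vs control | Ratio | Chance of a false difference, 154 per group | 308 per group |
|---|---|---|---|---|
| 85% | 19.0% vs 17.0% | 1.12 | 7% | 9% |
| 70% | 19.0% vs 14.0% | 1.36 | 22% | 39% |
| 50% | 19.0% vs 10.0% | 1.90 | 61% | 89% |

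**4. Deaths after discharge.** Let m be true mortality, f the share of all counted deaths that occur after discharge, and c the share of those that the chart captures. Control rate = m(1 − f) + m·f·c; the SINK rate is m if the calls find every death. With m = 10%:

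- c = 0, f = 5% to 30%: controls 9.5% to 7.0%, ratio 1.05 to 1.43.
- c = 0.5, same f: controls 9.75% to 8.5%, ratio 1.03 to 1.18.
- If 25% of deaths follow discharge and only 10% to 20% of those are missed: 1/(1 − 0.025) = 1.03 to 1/(1 − 0.05) = 1.05.
- If the calls are not used at all, no gap arises from them.

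**The case against.** The strongest case on the other side has five parts.

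- **Routine care may have been just as intensive.** The documents give no routine lab frequency, and Research Design expects treating-team labs to stand in for study labs. This stands as a limit on size: the lab gap could be small. It does not remove the asymmetry, because substitution avoids duplicate draws in SINK and adds none for controls.
- **SINK status is also abstracted from the chart.** True, but protocol labs drawn in hospital would probably be in that chart.
- **The calls may not enter at all.** The evaluation is called a chart analysis and nothing says that call data are used. This stands, so the point about deaths is conditional.
- **Direction is not settled.** A reader might infer that detection is always higher in SINK and that the comparison is therefore always biased against the study drugs. The documents do not support that: the schedule becomes weekly, and scoring SINK on it alone could reverse the sign.
- **Lab dependence is partial.** RIFLE also uses urine output, and cytokine storm also uses imaging, ventilation and fever. This stands for those two outcomes; liver failure rests on labs alone.

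A sixth remark concerns the remedy: the study team watches for rising oxygen needs in SINK patients, so advanced oxygenation may be noticed sooner there. That is met by scoring it from charted respiratory support in both groups.

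**Conclusion.** The concern holds as a gap that can be expected to bias specific outcomes of one supplementary comparison. The plan compares study outcomes across groups that it observes differently and sets no common rule. Liver failure, renal failure and cytokine storm are exposed. Post-discharge death is exposed only if call data are used.

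The size cannot be derived from the documents. The ratios in the working, including 1.5 to 2.0 for labs and 1.03 to 1.43 for deaths, are illustrations under assumed lab gaps, detection rates and shares of late deaths; the lab ratios of 1.5 to 2.0 apply only to daily-draw periods. More complete detection in SINK is likely in those periods. Over a whole stay the ratio could fall on either side of 1, depending on how SINK is scored.

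A reader might also infer that the randomized result is compromised. It is not: the naltrexone and placebo arms share the same lab schedule and calls, so the primary analysis and the randomized secondary comparisons are unaffected by this point.

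**What to change.** In the Statistical Analysis section, at the paragraph on the matched comparison, state that:

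- it is limited to in-hospital outcomes taken from the same chart sources in both groups: in-hospital death, advanced oxygenation from charted respiratory support, ICU admission, intubation and length of stay;
- liver failure, renal failure and cytokine storm are excluded from it;
- post-discharge death is included only if one source that does not use the study calls is applied to both groups.

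Scoring only labs ordered by the treating team is not a safe alternative, because study draws may replace clinical orders in SINK patients and lead to an undercount there.

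The change takes a few lines of text and needs no new data unless a common death source is added. The cost is fewer outcomes in a supplementary comparison; the excluded outcomes remain available in the randomized comparison.
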